## Clinical Investigation Plan

	

11. Severe ventricular dysfunction with LVEF <25% as measured by resting echocardiogram

12. Pre-existing prosthetic heart valve or other implant in any valve position, prosthetic ring, severe circumferential mitral annular calcification (MAC) which is continuous with calcium in the left ventricular outflow tract (LVOT), severe (greater than or equal to 3+) mitral insufficiency, or severe mitral stenosis with pulmonary compromise

13. Echocardiographic or multi-slice computed tomography (MSCT) evidence of intracardiac mass, thrombus or vegetation

14. Significant aortic disease, including abdominal aortic or thoracic aneurysm defined as maximal luminal diameter 5cm or greater; marked tortuosity (hyperacute bend), aortic arch atheroma (especially if thick [<math>> 5</math> mm], protruding or ulcerated) or narrowing (especially with calcification and surface irregularities) of the abdominal or thoracic aorta, severe “unfolding” and tortuosity of the thoracic aorta (applicable for transfemoral access only)

15. Aortic root angulation <math>> 70^\circ</math>

16. Undue risk of coronary obstruction (e.g., bulky aortic valve leaflets in close proximity to coronary ostia)

17. Non-calcified aortic annulus

18. Iliofemoral vessel characteristics that would preclude safe insertion of the FlexNav™ Delivery System with or without an arterial introducer sheath such as severe obstructive calcification, protruding thrombus or severe tortuosity (applicable for transfemoral access only)

19. Severe tricuspid regurgitation or severe right ventricle dysfunction

20. Minimum access vessel diameter of <math><5.0</math>mm for small FlexNav Delivery System and <math><5.5</math> mm for large FlexNav Delivery System

--	---

## Statistical Analysis Plan

### 1.0 SYNOPSIS OF STUDY DESIGN

#### 1.1 Purpose of the Statistical Analysis Plan

This statistical analysis plan (SAP) is intended to provide a detailed and comprehensive description of the planned methodology and analysis to be used for Portico NG clinical investigation plans (CIP) [REDACTED]. This plan is based on [REDACTED] the CIP.

#### 1.2 Clinical Investigation Objectives

The primary objective of this clinical study is to evaluate the acute safety and effectiveness of the Navitor Transcatheter Aortic Heart Valve as assessed by the rate of all-cause mortality at 30 days and the rate of moderate or greater paravalvular leak at 30 days. The results for the primary safety endpoint will be descriptively compared to published data on FDA approved TAVR devices, and the results for the primary effectiveness endpoint will be compared to a performance goal derived from published results of FDA approved TAVR devices studied in the same patient population (e.g., high and extreme surgical risk).

#### 1.3 Clinical Investigation Design

The Portico NG Approval study is a prospective, multi-center, international, single-arm investigational study designed in accordance with ISO standards 14155:2011 and 5840-3:2013. To be eligible for study participation, a patient must have symptomatic, severe native aortic stenosis and be considered high or extreme risk for surgical valve replacement. Implanting physicians must either have prior Portico TAVI system experience or must complete roll-in cases. Upon provision of informed consent and approval by the subject selection committee, subjects will undergo Navitor Valve implantation via a transfemoral or alternative access approach according to the site's anesthesia protocol for TAVR procedures.

To ensure sufficient number of subjects for primary endpoint analysis (described in detail in section 2.4), a total of [REDACTED] subjects may undergo a Navitor implant attempt in the PMA cohort for the 23-29mm Navitor sizes (Portico NG cohort).

A separate cohort of 60 subjects (Titan cohort) will undergo an implant attempt with the Navitor Titan valve. Data from the Titan cohort will be analyzed separately to support submissions for regulatory approval. Prospective data from Titan subjects enrolled under a separate, regional OUS protocol may be combined with US subjects to meet the minimum required sample size for the PMA submission. Importantly, both protocols enroll high and extreme surgical risk subjects with severe symptomatic AS who undergo Navitor Titan valve implantation with the FlexNav Delivery System in a premarket setting and are aligned in terms of inclusion/exclusion criteria, devices being studied, training requirements and Instructions for Use, follow-up requirements and data collection. Furthermore, subjects enrolled in the Titan cohort will undergo the same screening, baseline, procedure and follow-up assessments as the Portico NG cohort.

In addition, up to a total of 20 roll-in subjects may be enrolled and undergo a Navitor implant attempt.

Subjects participating in the clinical study will be followed for a total of 5 years with data collected at screening, baseline, procedure, prior to hospital discharge, and follow-up at 30 days, 12 months and annually thereafter up to 5 years. The expected duration of enrollment is 12 months, and the total duration of the clinical study is expected to be 6.5 years. Global regulatory submissions for the Navitor Titan valve will be completed when 60 subjects have 30-day follow-up data. Follow-up data through 5 years will be submitted as part of a final report to respective regulatory agencies.

## Statistical Analysis Plan

### 1.4 Endpoints

This clinical study has two (2) co-primary endpoints. The same primary endpoints will be evaluated in both the Portico NG and Titan cohorts and analyzed independently for each cohort.

#### 1.4.1 Primary Safety Endpoint

The primary safety endpoint is all-cause mortality at 30 days.

#### 1.4.2 Primary Effectiveness Endpoint

The primary effectiveness endpoint is moderate or greater paravalvular leak at 30 days.

#### 1.4.3 Secondary Endpoint

This clinical study has one secondary endpoint, a non-hierarchical composite of all-cause mortality, disabling stroke, life threatening bleeding, acute kidney injury (stage 3), or major vascular complications at 30 days. The secondary endpoint is the same for the Titan cohort as the Portico NG cohort and will be analyzed independently for each cohort.

#### 1.4.4 Descriptive Endpoints

The following key outcomes (relevant to characterizing the safety profile and outcomes based on the design modifications) will be assessed as descriptive endpoints for the study (for both the Portico NG and Titan cohorts, but analyzed independently for each cohort):

- Technical device success defined as successful vascular access, delivery and deployment of the Portico NG Valve; retrieval with the delivery system and correct positioning of a single valve in the proper anatomical location and the absence of procedural mortality
- All-cause mortality at 12 months from the index procedure
- Cardiovascular-related mortality at 30 days and 12 months from the index procedure
- Disabling stroke at 30 days and 12 months from the index procedure
- Life threatening and major bleeding at 30 days from the index procedure
- Acute kidney injury at 30 days from the index procedure
- Major and minor vascular complications at 30 days from the index procedure
- Permanent pacemaker insertion at 30 days and 12 months from the index procedure
- Changes in functional status from baseline to follow-up assessments at 30 days and 12 months (e.g., NYHA classification, six-minute walk test, quality of life measures)
- Paravalvular leak at discharge, 30 days and 12 months from the index procedure
- Changes in echocardiographic parameters from baseline to follow-up at 30 days and 12 months (e.g., mean effective orifice area, mean transvalvular gradient, mean peak velocity)
- Symptomatic valve thrombosis at 30 days and 12 months from the index procedure

## Statistical Analysis Plan

Additional outcomes to be collected and assessed during the study:

- Myocardial infarction at 30 days and 12 months from the index procedure
- New-onset atrial fibrillation at 30 days and 12 months from the index procedure
- Coronary obstruction requiring intervention at 30 days from the index procedure
- Valve embolization during procedure, and at 30 days and 12 months from the index procedure
- Reintervention to treat valve-related dysfunction at 30 days and 12 months from the index procedure
- Total aortic valve regurgitation (transvalvular plus paravalvular leak) at discharge, 30 days and 12 months from the index procedure

## 2.0 **ANALYSIS CONSIDERATIONS**

### 2.1 **Analysis Populations**

#### 2.1.1 **Attempted Population**

The attempted population will include all subjects in whom a Navitor implant is attempted, excluding roll-in cases. A Navitor implant attempt is defined as insertion of the FlexNav™ Delivery System (loaded with a Navitor valve) into the subject's vasculature.

#### 2.1.2 **Implanted Population**

The implanted population will include all subjects in the attempted population excluding any subject with competitor valve implanted or subject without a valve implanted.

### 2.2 **Statistical Methods**

#### 2.2.1 **Descriptive Statistics for Continuous Variables**

For continuous variables (e.g., age, BMI, heart rate, etc.), results will be summarized with the numbers of observations, means, and standard deviations, with quartiles, minimums, maximums, and 95% confidence intervals for the means, when specified.

#### 2.2.2 **Descriptive Statistics for Categorical Variables**

For categorical variables (e.g. gender, diabetic status, etc.), results will be summarized with subject counts and percentages/rates, with exact 95% Clopper-Pearson confidence intervals, when specified.

#### 2.2.3 **Survival Analyses**

Survival analysis will be conducted to analyze time-to-event variables. Subjects without events will be censored at the time of analysis. Survival curves will be constructed using Kaplan-Meier estimates and Greenwood standard errors.

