## Clinical Investigation Plan

### 5.4 Subject Enrollment

The point of a subject's enrollment in the clinical study is completion of signing the informed consent.

Consented subjects who undergo study-specific testing and are found to have met exclusion criteria or not all inclusion criteria (or if a site disagrees with the Subject Selection Committee's decision regarding risk classification) will be considered screen failures; these subjects will not be counted toward the sample size of 169 analysis subjects and will be exited from the study without further follow-up.

In addition, consented subjects who undergo study-specific testing and meet study criteria but do not undergo a Navitor implant attempt (defined as insertion of the delivery system into the vasculature) will not be counted toward the sample size of 169 analysis subjects and will be exited from the study without further follow up.

All subjects who undergo a Navitor implant attempt will be included in the analysis population or designated as roll-in as described in Section 5.4.1. Subjects who undergo a Navitor implant attempt but are not implanted with the Navitor Valve will be followed for 30 days and then exited from the study; similarly, any subject who undergoes explant of the Navitor Valve during the study follow-up period will be exited from the study 30 days following the explant procedure.

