### 5.5 Subject Withdrawal

Each enrolled subject shall remain in the clinical study until completion of the required follow-up period; however, a subject's participation in any clinical study is voluntary and the subject has the right to withdraw at any time without penalty or loss of benefit. Conceivable reasons for discontinuation may include, but not be limited to, the following:

- Subject death
- Subject voluntary withdrawal
- Subject lost-to follow-up as described below
- Subject's follow-up is terminated according to Section 3.3.

The Sponsor must be notified by the site of subject's discontinuation as well as the reason(s) for subject discontinuation. Investigators must also report subject discontinuations to their respective IRB/EC as defined by their institution's procedure(s).

No additional follow-up will be required or data recorded from subjects once withdrawn from the clinical study. However, if a subject withdraws from the study due to problems related to the safety or performance of the device under investigation, the investigator shall ask for the subject's permission to follow his/her status/condition outside of the clinical study.

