### 5.6 Number of Subjects

A total of 169 analysis subjects (up to a total of 189 subjects including roll-ins) will undergo an attempted Navitor implant in order to analyze the primary endpoints for the Portico NG cohort. Furthermore, a total of 60 analysis subjects will undergo an attempted Navitor Titan implant for the PMA submission. To ensure

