### 8.4 Timing of Analysis

The analysis for the PMA submission will be conducted on a dataset locked after a minimum of 152 analysis subjects in the Portico NG cohort have had a 30-day study visit and have PVL data assessed by the echocardiography core laboratory. As stated in section 3, an analysis of the first 80 subjects (with a Navitor implant attempt) with 30-day follow-up data will be provided to support the CE Mark submission.

Data from the Titan cohort will be analyzed independently from the Portico NG cohort. The analysis for the Titan cohort will be conducted on a dataset locked after 60 analysis subjects have had a 30-day study visit and have PVL data assessed by the echocardiography core laboratory, excluding any subjects who die or are lost to follow-up within 30 days.

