### 2.3 Endpoint Analysis

#### 2.3.1 Primary Endpoints

##### 2.3.1.1 Primary Safety Endpoint (Portico NG cohort)

The primary safety endpoint for the Portico NG cohort is all-cause mortality at 30 days post index procedure.

The proportion of Portico NG subjects experiencing a primary safety endpoint will be estimated from the binomial model. COVID-19 relatedness of mortality will be adjudicated by the Clinical Events Committee (CEC), and any 30-day death that is adjudicated as COVID-19 related will be excluded from the primary analysis (i.e., from both numerator and denominator). The 95% confidence intervals will be calculated using the exact Clopper-Pearson method. The estimated primary safety endpoint rate at 30 days will be descriptively compared with the all-cause mortality rates (and 95% confidence intervals) of FDA approved TAVR devices studied in the same patient population (e.g., high and extreme risk), and additional published data on high and extreme surgical risk subjects available at the time of PMA submission, as described in the CIP.

The analysis population will include subjects who undergo a Navitor implant attempt that is described in Section 2.1.1, including subjects who withdraw or are lost to follow-up prior to 30-day visit.

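### The SAP's single censoring date keeps subjects at risk after their observation has ended, and unknown day-30 status adds no event; both effects are small and fixable by wording

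*SAP*

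**What the plan says.** **Censoring.** SAP 2.2.3 sets the rule for all time-to-event analyses: "Subjects without events will be censored at the time of analysis". It names no other date.

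**When observation ends.** Protocol 5.4 says that subjects with an attempt "but are not implanted with the Navitor Valve will be followed for 30 days and then exited from the study", and that an explanted subject "will be exited from the study 30 days following the explant procedure". Protocol 5.5 adds: "No additional follow-up will be required or data recorded from subjects once withdrawn from the clinical study". The listed endpoints run to 12 months, for example "All-cause mortality at 12 months from the index procedure" (SAP 1.4.4).

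**Safety denominators.** The primary safety endpoint is a binomial proportion in the attempted population, "including subjects who withdraw or are lost to follow-up prior to 30-day visit" (SAP 2.3.1.1). SAP 2.3.1.2 (Titan) and 2.3.2 (secondary composite) say the same. Protocol 8.8 plans no imputation, while SAP 2.9 says that analyses use available data.

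**Titan.** Protocol 8.11 defines success as at most 3 deaths within 30 days in 60 analysis subjects. Protocol 5.6 says that "a total of 60 analysis subjects will undergo an attempted Navitor Titan implant for the PMA submission". The lock rule (Protocol 8.4, SAP 2.6) instead counts 60 subjects with a 30-day visit and core-laboratory PVL data, and sets aside those who die or are lost within 30 days.

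**Subgroups.** SAP 2.8 allows optional subgroup analyses with Kaplan-Meier estimates for both primary endpoints. Protocol 8.5 plans none.

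**The concern.** A Kaplan-Meier estimate is valid only if the risk set contains people who could be seen to have an event. A subject who exits at day 30 but is censored at the analysis date sits in every later risk set without being able to contribute an event, so the estimated event rate can only fall.

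The binomial safety endpoints have a related weakness. Someone whose day-30 status is unknown stays in the denominator and adds nothing to the numerator, so is in effect counted as event-free. For most rates this is minor. Titan success, however, is a raw death count, so a single unknown subject could matter at the limit. The sensitivity analyses in SAP 2.13 address only COVID-19 relatedness and would not show this.

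Finally, PVL is one status reading with no event time. Kaplan-Meier adds nothing to it and can give an uninformative interval in a small subgroup.

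**Working it through.** **1. Censoring bias.** The documents give no 12-month mortality or attrition, so these are assumptions: mortality 10-15% and loss 2-10% per year, independent and exponential with hazards L and M.

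- True rate at time t: 1 - exp(-Lt).
- Rate under the literal rule: L/(L+M) × (1 - exp(-(L+M)t)).

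| Death / loss per year | True 12-month rate | Literal rule | Understated by |
|---|---|---|---|
| 10% / 2% | 10.00% | 9.90% | 0.10 points |
| 10% / 5% | 10.00% | 9.75% | 0.25 points |
| 10% / 10% | 10.00% | 9.50% | 0.50 points |
| 15% / 2% | 15.00% | 14.85% | 0.15 points |
| 15% / 10% | 15.00% | 14.26% | 0.74 points |

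For scale, sqrt(p(1-p)/169) is 2.31 points at 10% and 2.75 at 15%. At day 30 the same formulas differ by 0.0007 to 0.0057 points. With M = 0 the difference is zero.

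Protocol-mandated day-30 exits alone, for an assumed k of 169 subjects, give a bias of (k/169) × (q12 - q30)/(1 - q30), where q12 and q30 are mortality at 12 months and 30 days. For k = 1 to 5 this is 0.05 to 0.27 points at 10% mortality and 0.08 to 0.41 at 15%.

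**2. Unknown day-30 status, Titan.** The plan's own limit is 3/60 = 5.0% (Clopper-Pearson 95% interval 1.0-13.9%). The visible text gives no derivation of the limit, so only its behaviour can be checked. With 3 known deaths and 1 unknown:

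- As written: 3/60 = 5.0%, pass.
- Kaplan-Meier at day 30, unknown subject censored before the first death: 3/59 = 5.1%.
- Worst case: 4/60 = 6.7% (1.8-16.2%), over the limit.

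Protocol 1.1.1 reports 30-day mortality of 1.4-4.2% for comparable devices. The binomial probability of exactly 3 deaths among 59 known subjects is 4.05% at 1.4% and 21.8% at 4.2%. Multiplying by the unknown subject's own risk gives the chance that a fourth death is hidden: 4.05% × 0.014 = 0.06%, and 21.8% × 0.042 = 0.9%. If loss is related to death, the multiplier is larger.

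The two readings of the lock rule give 3/60 = 5.0% if deaths are merely excused from the visit, and 3/63 = 4.8% if 60 completers are needed besides 3 deaths.

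**3. PVL subgroups.** With no events, every term of Greenwood's sum, d/(n(n-d)), is zero, so a plain interval has zero width; a log-log interval is undefined at S = 1. The two-sided 95% Clopper-Pearson upper limit is 30.8% for 0/10 and 8.8% for 0/40. These sizes are the minimum counts in Protocol 3 for the 23 mm valve and for the 23 and 25 mm valves together, not expected sizes. At the 3.9% moderate PVL rate quoted in Protocol 1.1.1 for the Portico I study, the chance of no events is 0.961^10 = 67% and 0.961^40 = 20%.

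**The case against.** The strongest reply is that the censoring sentence has almost no consequence. The primary and secondary endpoints are binomial. The only named endpoints that the SAP assigns to Kaplan-Meier are the primary endpoints in optional subgroups, both at day 30, where the bias is under 0.01 points. No passage assigns Kaplan-Meier to the 12-month endpoints or specifies a 5-year curve. This stands and makes the point minor. It does not rescue the sentence, because SAP 2.2.3 covers time-to-event variables generally and the available-data clause supplies no other date.

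Several stronger readings are tempting but unsupported:

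- **That a success criterion or the Portico NG PVL test is biased by censoring.** That test is a binomial upper bound against 8.5% in subjects with a core-laboratory reading. No censoring date enters it.
- **That day-30 exits create unknown day-30 status.** Protocol 5.4 exits occur no earlier than day 30. Only earlier withdrawal or loss can do this, and Protocol 5.5.1 lets vital status come from a general practitioner or relative.
- **That the Portico NG shortfall in PVL data measures unknown survival.** The lock needs "a minimum of 152 analysis subjects in the Portico NG cohort have had a 30-day study visit and have PVL data", against 169 attempts. A missed or unreadable echocardiogram, or a visit not yet due, does not make survival unknown.
- **That the cure is a rate among subjects with known status.** Keeping leavers who had an event and dropping those who did not biases the rate upward. In the model above, with day-30 mortality 4.2% and an assumed 5% loss by day 30, observed deaths are about 4.1% and known survivors 0.958 × 0.95 = 91.0%. The known-status rate is then 4.31%, too high by about as much as the plan is too low.

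The available-data clause might also be read as removing unknown subjects from the denominator. That would conflict with SAP 2.3.1.2, and the Titan death count would still gain nothing.

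**Conclusion.** SAP 2.2.3 is wrong as written, with a small effect. Kaplan-Meier estimates beyond day 30 are biased low if anyone leaves: 0.1-0.7 points at 12 months under the assumed rates, well inside one standard error.

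The treatment of unknown day-30 status matters chiefly at the Titan limit. There, one unknown subject alongside exactly 3 known deaths leaves the verdict open. For one unknown subject of equal risk, the chance of a hidden fourth death is 0.06-0.9%, and higher if loss is related to death. The Titan denominator is stated in two ways that need reconciling.

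The subgroup point is conditional on optional analyses that the protocol does not plan. Overall severity is minor.

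**What to change.** - **SAP 2.2.3:** censor event-free subjects at the earliest of last contact with known event-free status, study exit or data cut-off.
- **SAP 2.3.1.1, 2.3.1.2, 2.3.2:** keep the attempted-population rate as primary. Report the number with unknown day-30 status (vital status for the mortality endpoint), and add a worst-case line counting unknowns as events; for Titan, apply it to the 3-death limit. A day-30 Kaplan-Meier estimate with the corrected censoring may be added. Reconcile SAP 2.9 with these sections.
- **Protocol 8.4 and SAP 2.6:** state whether the Titan 60 are all attempts, as in Protocol 5.6 and 8.11, or completers.
- **SAP 2.8:** if subgroups are run, give PVL as proportions with Clopper-Pearson intervals and reserve Kaplan-Meier for mortality.

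The cost is a few sentences and no new data collection. Later Kaplan-Meier rates may look slightly less favourable, and the Titan worst-case line could show a count above the limit.

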### 2.3.2 Secondary Endpoint

The secondary endpoint is a non-hierarchical composite of all-cause mortality, disabling stroke, life threatening bleeding, acute kidney injury (stage 3), or major vascular complications at 30 days. This endpoint will be analyzed for both the Portico NG and Titan cohorts separately.

The proportion of subjects experiencing a secondary endpoint will be estimated from the binomial model. COVID-19 relatedness of secondary endpoint events will be adjudicated by the CEC, and any 30-day secondary endpoint event that is adjudicated as COVID-19 related will be excluded from the primary analysis (i.e., from both numerator and denominator). The 95% confidence intervals will be calculated

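### SAP 2.2.3 gives Kaplan-Meier as the only time-to-event method and no rule for death before the event, so later non-fatal and cardiovascular-death rates can be misestimated in either direction

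*SAP*

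**What the plan says.** SAP 2.2.3 is the whole of the survival plan. It states "Survival analysis will be conducted to analyze time-to-event variables", then "Subjects without events will be censored at the time of analysis", then "Survival curves will be constructed using Kaplan-Meier estimates and Greenwood standard errors". It does not list the variables, and it gives no rule for death before a non-fatal event or for non-cardiovascular death before cardiovascular death. Neither document names a competing-risk method.

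The outcomes that death can preclude are in SAP 1.4.4, for example "Cardiovascular-related mortality at 30 days and 12 months from the index procedure". Disabling stroke, pacemaker, symptomatic valve thrombosis, myocardial infarction, new-onset atrial fibrillation, valve embolization and reintervention also run to 12 months. SAP 2.3.3 assigns an analysis population to the descriptive endpoints but no estimator. No event endpoint is listed beyond 12 months, although SAP 1.3 says "Follow-up data through 5 years will be submitted as part of a final report".

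Elsewhere the plan uses proportions. For primary safety in the Portico NG cohort, "The proportion of Portico NG subjects experiencing a primary safety endpoint will be estimated from the binomial model". For the composite, "The proportion of subjects experiencing a secondary endpoint will be estimated from the binomial model". For categorical variables, "results will be summarized with subject counts and percentages/rates, with exact 95% Clopper-Pearson confidence intervals, when specified". Kaplan-Meier is tied to named endpoints only in SAP 2.8, for optional subgroup analyses of the primary endpoints.

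**The concern.** The cohort is at high or extreme surgical risk, has an expected average age above 80 (Protocol 5.4.3) and is followed for 5 years. Many subjects will die without having had a stroke, a reintervention or another non-fatal event. If those subjects are censored at death, 1-KM estimates the risk as if other deaths did not occur, and this exceeds the proportion of patients who have the event. If instead they stay in the risk set until the analysis date, together with subjects lost to follow-up, the lost subjects count as observed and event-free, and the estimate falls below the true incidence.

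At stake are the descriptive 12-month rates and any event curves in the 5-year final report. The text of SAP 2.2.3 allows rules that give different answers, and the choice would be made with data in hand.

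**Working it through.** The documents give no figure on this point, so there is none to reproduce.

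**Inputs.** The 30-day mortality range of 1.4%-4.2% for newer devices comes from Protocol 1.1.1. The documents give no expected 12-month or 5-year mortality for this cohort, no long-term event rates and no loss rate. These are assumptions: mortality 10%-15% at 12 months and 50% at 5 years, with wider ranges in step 3.

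**Model.** Constant, independent hazards *h* (event), *d* (competing death) and *l* (loss), with *d* = -ln(1 - mortality)/T.
- True cumulative incidence: CIF = h/(h+d) × (1 - exp(-(h+d)T)).
- Deaths censored at death: 1-KM = 1 - exp(-hT).
- Dead and lost subjects kept at risk to the analysis date: the estimate tends to h/(h+d+l) × (1 - exp(-(h+d+l)T)).

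**Step 1. Deaths censored at death.** Solve for *h* at a given true CIF, then read 1-KM.

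| T | Mortality | d per year | True CIF | h per year | 1-KM |
|---|---|---|---|---|---|
| 12 months | 10% | 0.1054 | 5.0% | 0.0541 | 5.3% |
| 12 months | 15% | 0.1625 | 5.0% | 0.0557 | 5.4% |
| 12 months | 15% | 0.1625 | 10.0% | 0.1145 | 10.8% |
| 5 years | 50% | 0.1386 | 5.0% | 0.0143 | 6.9% |
| 5 years | 50% | 0.1386 | 10.0% | 0.0296 | 13.7% |

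Check of the last row: 0.029575/0.168205 × (1 - exp(-0.8410)) = 10.0%, and 1 - exp(-0.1479) = 13.7%.

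**Step 2. Dead and lost subjects kept at risk.** Take T = 5, h = -ln(0.80)/5 = 0.0446 and d = -ln(0.50)/5 = 0.1386.
- True CIF: 0.0446/0.1833 × (1 - exp(-0.9163)) = 14.6%. Censoring at death would give 20%.
- No loss (l = 0): the estimate is 14.6%, which is correct.
- 5% yearly loss (l = -ln(0.95) = 0.0513): 0.0446/0.2346 × (1 - exp(-1.1728)) = 13.1%, an understatement of about 1.5 points. Simulation of 400,000 subjects with l = 0.05 gave 13.2%.

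**Step 3. Wider ranges for censoring at death.**
- 30 days, mortality 1.4%-4.2%, 1-KM of 3%-20%: excess 0.02 to 0.41 points.
- 12 months, mortality 5%-25%, 1-KM of 3%-20%: excess 0.1 to 2.5 points. The 25% upper bound is the untreated yearly figure in Protocol 1.1.1.
- 5 years, mortality 30%-70%, 1-KM of 5%-30%: excess 0.8 to 12 points.

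**Step 4. Front-loaded events such as pacemaker.** Assume 15% with the event and 2% mortality by 30 days, then an event hazard of 0.015 per year. 1-KM against CIF is 16.3% against 16.2% at 12 months (10% mortality) and 21.1% against 19.4% at 5 years (50% mortality).

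**The case against.** The strongest objection is that the SAP never says these endpoints are analysed by Kaplan-Meier. A reader might infer that non-fatal events and cardiovascular death are. But SAP 2.2.3 lists no variables, SAP 2.3.3 names no estimator, and where methods are stated they are mostly proportions: the composite is binomial, and adverse events in SAP 3.2 are counts and percentages. This stands, so the point applies only to outcomes that are in fact analysed under SAP 2.2.3.

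A reader might also infer that event rates will be overstated. The censoring sentence does not support that certainty, because it does not censor the dead at death. Read literally, it keeps every event-free subject at risk to the analysis date. That does not rescue the plan: this reading matches cumulative incidence only with no dropout and is too low otherwise (step 2).

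Further limits stand. The listed event endpoints stop at 12 months, where the excess is small beside sampling error: with n = 169 the approximate 95% half-width, 1.96 × sqrt(p(1-p)/n), is 3.3 points at 5% and 4.5 points at 10%, and it is wider with n = 60. Constant hazards exaggerate the error for procedure-related events. For cardiovascular death only non-cardiovascular death competes, so figures based on total mortality are too large there.

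**Conclusion.** The point holds as a gap in specification with a possible error in either direction. For a non-fatal event or cardiovascular death analysed under SAP 2.2.3, censoring at death overstates by about 0.3 to 0.8 points at 12 months with 10%-15% mortality. At 5 years with 50% mortality, a true 10.0% reads 13.7%. Keeping dead and lost subjects at risk makes a true 14.6% read about 13.1% at 5 years with 5% yearly loss. All of these rest on assumed mortality, event and loss rates and on constant hazards. The 5-year figures concern curves that the SAP does not define.

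The documents do not support an inference that device comparisons or trial success are distorted. The SAP specifies comparisons with other devices only for the 30-day primary and secondary endpoints. Those are binomial proportions, and the success criteria in SAP 2.7 rest on 30-day death and paravalvular leak. All-cause death has no competing death. This is a cheap improvement to descriptive reporting, not a threat to the main conclusions.

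**What to change.** Amend SAP 2.2.3 as follows:
- List the outcomes to be analysed as time-to-event.
- Censor living event-free subjects at last contact.
- Keep Kaplan-Meier for all-cause mortality.
- For every other time-to-event outcome at 12 months and later, report the Aalen-Johansen cumulative incidence, with death as the competing event (non-cardiovascular death for cardiovascular mortality).
- Show Kaplan-Meier beside it where a published comparator used Kaplan-Meier.

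The cost is a few sentences and a standard option in the SAS version named in SAP 4.0, using data already collected. No endpoint, sample size or success rule changes. The small downside is two figures for some endpoints, which the report would need to label clearly.
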